4.1. Protocol Deviations

Important protocol deviations (including deviations related to study inclusion/exclusion criteria, conduct of the trial, patient management or patient assessment) will be summarised and listed. (Please refer to [Appendix 1: Protocol Deviation Management](#)).

Protocol deviations will be tracked by the study team throughout the conduct of the study in accordance with the most current Protocol Deviation Management Plan.

- Data will be reviewed prior to unblinding and freezing the database (DBF) to ensure all important deviations are captured and categorised on the protocol deviations dataset.
- This dataset will be the basis for the summaries and listings of protocol deviations.
- A separate summary and listing of all inclusion/exclusion criteria deviations will also be provided. This summary will be based on data as recorded on the inclusion/exclusion page of the electronic case report form (eCRF).

5. CONSIDERATIONS FOR DATA ANALYSES AND DATA HANDLING CONVENTIONS

5.1. Study Treatment & Sub-group Display Descriptors

Treatment Group Descriptions			
RandAll NG System		Data Displays for Reporting	
Code	Description	Description	Order in TLF
PBO	Placebo	Placebo	1
DNX	GSK1325756 (danirixin) 35mg HBr	DNX 35mg HBr	2

Treatment comparisons will be displayed as follows using the descriptors as specified:
Danirixin vs. Placebo

5.2. Baseline Definitions

For all endpoints (except as noted in baseline definitions) the baseline value will be the latest pre-dose assessment with a non-missing value, including those from unscheduled visits. If time is not collected, Day 1 assessments are assumed to be taken prior to first dose and used as baseline.

Parameter	Study Assessments Considered as Baseline		Baseline Used in Data Display
	Screening	Week 0/ Day 1	
FEV ₁ (All Spirometry)	X	X	Week 0/Day 1
SGRQ-C Total Score		X	Week 0/Day 1
SGRQ-C Domain Scores		X	Week 0/Day 1
CAT score		X	Week 0/Day 1
Vital Signs	X	X	Week 0/Day 1
ECG	X	X	Week 0/Day 1
Clinical Laboratory Assessments	X	X	Week 0/Day 1
Rescue Medication Use: Mean number of occasions per day	X	X	-7 to -1 (Mean during a stable period between 7 days before treatment start date (Week 0/Day 1) and day before Day 1 of study treatment. Data must be present on at least 4 days.)
Rescue Medication Use: Percentage of rescue-free days	X	X	-7 to -1 (Mean during a stable period between 7 days before treatment start date (Week 0/Day 1) and day before Day 1 of study treatment. Data must be present on at least 4 days.)

Unless otherwise stated, if baseline data is missing no derivation will be performed and baseline will be set to missing.

5.3. Spirometry and Rescue Medication Use Sources

5.3.1. Spirometry Sources

Clinic (centralized) spirometry collecting FEV₁ and FVC measurements (FEV%, and FVC% and FEV1/FVC will be calculated) will be performed in triplicate at time points listed in the SoA at the clinic. All spirometry values used and presented will be based on clinic spirometry.

Mobile (handheld) spirometry collecting FEV₁ and FVC parameters will also be performed weekly outside of clinic visits by the participants using a handheld spirometer at home.

5.3.2. Rescue Medication Use Sources

Rescue medication use will be collected via a daily diary over the course of the study.

Metered Dose Inhalers (MDI) sensor devices will be attached to participants’ rescue medications and the date and time of each use of rescue medication will be recorded and transmitted.

Both rescue medication use from daily diary and MDI sources will be reported.

5.4. Other Considerations for Data Analyses and Data Handling Conventions

Other considerations for data analyses and data handling conventions are outlined in the appendices:

Section	Component
10.3	Appendix 3: Assessment Windows
10.4	Appendix 4: Study Phases and Treatment Emergent Adverse Events
10.5	Appendix 5: Data Display Standards & Handling Conventions
10.6	Appendix 6: Derived and Transformed Data
10.7	Appendix 7: Reporting Standards for Missing Data
10.8	Appendix 8: Values of Potential Clinical Importance

6. STUDY POPULATION ANALYSES

6.1. Overview of Planned Study Population Analyses

The study population analyses will be based on the Safety Population, unless otherwise specified.

Study population analyses including analyses of participants' disposition, protocol deviations, medical history, demographic and baseline characteristics, prior and concomitant medications, and exposure will be based on GSK Core Data Standards. Details of the planned displays are presented in [Appendix 10: List of Data Displays](#).

7. EFFICACY ANALYSES

7.1. Primary Efficacy Analyses

7.1.1. Variables

7.1.1.1. FEV₁

Post-bronchodilator FEV₁ (L) (from clinic spirometry) to measure change in lung function will be summarized as specified in Section 7.1.2.

The table below shows the schedule of pre- and post-bronchodilator clinic spirometry assessments by visit.

Assessment	V1	V2	V3	V4	V5	V6	V7	V8	V9	V10	V11	V12	EW
	Pre-bronchodilator												
FEV ₁ (L)	X												
FVC (L)	X												
	Post-bronchodilator												
FEV ₁ (L)	X	X	X	X	X	X	X	X	X	X	X	X	X
FVC (L)	X	X	X	X	X	X	X	X	X	X	X	X	X

7.1.1.2. SGRQ Total Score

St. George Respiratory Questionnaire (SGRQ) total score derived from SGRQ-C at each scheduled visit will be summarized as specified in Section 10.5.2 and Section 10.6.3.

7.1.2. Summary Measure

Summary statistics, as specified in Section 10.5.2, for FEV₁ (L) and SGRQ total scores by treatment for each time point

7.1.3. Population of Interest

The primary efficacy analyses will be based on the Safety population, unless otherwise specified.

7.1.4. Strategy for Intercurrent (Post-Randomization) Events

Should any participant discontinue treatment (prior to project termination announcement), any recorded data up to the time of treatment discontinuation will be used in summaries.

Any intermittent missing data, not due to treatment discontinuation, will remain missing and any subsequent available data will be used.

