7.2. Secondary Efficacy Analyses

7.2.1. Variables

7.2.1.1. Spirometry

Percent predicted FEV₁, FVC (L) and FEV₁/FVC (from clinic spirometry) will be summarized as specified in Section [7.2.2](#).

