7.2.1.2. SGRQ Domain Scores

Raw and change from baseline SGRQ Domain scores will be summarized as specified in Section [7.2.2](#).

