7.2.1.3. CAT

Raw and change from baseline CAT scores will be summarized as specified in Section [7.2.2](#).

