10.7. Appendix 7: Reporting Standards for Missing Data

10.7.1. Premature Withdrawals

Element	Reporting Detail
General	
 Participant study completion (i.e. as specified in the protocol) was defined as completion of all phases of the study including the last study visit and the last scheduled procedure shown in the Schedule of Activities (Appendix 2) For the purposes of reporting, a participant is considered to have completed the study if they have not withdrawn and attended Visit 12 Withdrawn participants were not replaced in the study. All available data from participants who were withdrawn from the study will be listed and all available planned data will be included in summary tables and figures, unless otherwise specified. Withdrawal visits will be slotted as per Appendix 3: Assessment Windows or will be summarised as withdrawal visits.

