10.10.4. Efficacy Tables

Efficacy: Tables					
No.	Population	IDSL / Example Shell	Title	Programming Notes	Deliverable [Priority]
Spirometry					
2.1.	Safety	Based on PD4	Summary of Baseline Spirometry Measures	Post-BD FEV ₁ (L), Percent predicted normal post-BD FEV ₁ (%), Post-BD FVC (L), Post-BD FEV ₁ /FVC Transpose PD4 table to have treatment in columns and spirometry assessments in rows	SAC
2.2.	Safety	PD4	Summary of Post-Bronchodilator FEV ₁ (L)	Include raw and change from baseline	SAC
2.3.	Safety	PD4	Summary of Post-Bronchodilator FVC (L)	Include raw and change from baseline	SAC
SGRQ					
2.4.	Safety	PD4	Summary of Baseline SGRQ Scores	Total and domain scores	SAC
2.5.	Safety	PD4	Summary of SGRQ Scores by Visit	Include raw and change from baseline Total and domain scores	SAC
CAT					
2.6.	Safety	PD4	Summary of Baseline CAT Scores	Include total column	SAC
2.7.	Safety	PD4	Summary of CAT Score by Visit	Include raw and change from baseline	SAC
Rescue Medication Use					
2.8.	Safety	PD4	Summary of Baseline Mean Number of Puffs of Rescue Medication per Day using Diary Data	Include total column	SAC
2.9.	Safety	PD4	Summary of Baseline Percentage Rescue-free Days using Diary	Include total column	SAC

			Data		
2.10.	Safety	PD4	Summary of Mean Number of Puffs of Rescue Medication per Day using Diary Data in 4-week intervals		SAC
2.11.	Safety	PD4	Summary of Percentage Rescue-free Days using Diary Data in 4-week intervals		SAC
2.12.	Safety	PD4	Summary of Baseline Mean Number of Occasions of Rescue Use per Day using MDI Sensor Data	Include total column	SAC
2.13.	Safety	PD4	Summary of Baseline Percentage Rescue-free Days using MDI Sensor Data	Include total column	SAC
2.14.	Safety	PD4	Summary of Mean Number of Occasions of Rescue Use per Day using MDI Sensor Data in 4-week intervals		SAC
2.15.	Safety	PD4	Summary of Percentage Rescue-free Days using MDI Sensor Data in 4-week intervals		SAC

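### Does the treatment-discontinuation rule in SAP Section 7.1.4 put SGRQ total and its domains, or FEV1 and FVC, on different participants?

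*SAP*

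**What the plan says.** Section 7.1 (Primary Efficacy Analyses) covers post-bronchodilator FEV1 in litres and SGRQ total score. Its subsection 7.1.4 gives the rule for stopping treatment: "Should any participant discontinue treatment (prior to project termination announcement), any recorded data up to the time of treatment discontinuation will be used in summaries". A second paragraph deals with intermittent gaps that are not due to discontinuation. These stay missing, and later data are used.

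Section 7.2 (Secondary Efficacy Analyses) covers the companion measures: "Percent predicted FEV₁, FVC (L) and FEV₁/FVC (from clinic spirometry) will be summarized as specified in Section" 7.2.2, "Raw and change from baseline SGRQ Domain scores will be summarized as specified in Section" 7.2.2, and "Raw and change from baseline CAT scores will be summarized as specified in Section" 7.2.2. It repeats the subsections on variables, summary measure, population and methods, but has none on intercurrent events.

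Section 10.7.1 (Premature Withdrawals) gives a general default for participants withdrawn from the study: "all available planned data will be included in summary tables and figures, unless otherwise specified". It also says: "All available data from participants who were withdrawn from the study will be listed".

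In Appendix 10, Table 2.5 carries all SGRQ scores by visit, with the programming note "Include raw and change from baseline Total and domain scores". Section 2.4 says that early termination rules out any formal analysis and that the primary and secondary endpoints will be shown as summary statistics.

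**The concern.** Section 7.2 restates even the population and the descriptive-statistics sentence from 7.1, so it does not seem to inherit from 7.1. The intercurrent-event rule is the subsection left out. Read that way, 7.1.4 governs only FEV1 and SGRQ total, and everything else falls to the 10.7.1 default.

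Take a participant who stops treatment before the announcement and is assessed later, for example at the early withdrawal (EW) visit. FEV1 and FVC are both scheduled there in 7.1.1.1. FEV1 would leave Table 2.2 while FVC from the same visit stayed in Table 2.3. SGRQ total would leave Table 2.5 while the three domains from the same questionnaire stayed in it. Participants stopped by the termination itself would keep all of these values, because the rule names only earlier stops. Rescue medication use has a further rule in 10.6.3, ending the day before the treatment stop date.

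At stake would be the coherence of the tables holding the two primary variables. No efficacy listing is planned from which the dropped values could be recovered.

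**Working it through.** **Which rule would govern each by-visit variable, read by heading alone**

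| Table | Variable | Named in | Rule |
|---|---|---|---|
| 2.2 | FEV1 | 7.1.1.1 | 7.1.4 |
| 2.3 | FVC | 7.2.1.1 | 10.7.1 |
| 2.5 | SGRQ total | 7.1.1.2 | 7.1.4 |
| 2.5 | three SGRQ domains | 7.2.1.2 | 10.7.1 |
| 2.7 | CAT | 7.2.1.3 | 10.7.1 |

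That gives 1 + 1 + 1 + 3 + 1 = 7 variables, 2 under 7.1.4 and 5 under the default. Percent predicted FEV1 and FEV1/FVC appear in Appendix 10 only at screening and baseline (Tables 1.15 and 2.1), so they have no by-visit row to disagree with.

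**Does the text produce the split?**

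1. *Exclusion of later data.* 7.1.4 says which data are used. It does not say that later data are removed. Its second paragraph makes a cut the more natural reading, but this is still an inference.
2. *Retention of the secondary measures.* The 10.7.1 default concerns withdrawal from the study, whereas 7.1.4 concerns stopping treatment. The SAP reports the two separately (Tables 1.1 and 1.3, Listings 2 and 3). For someone who stops treatment but stays in the study, 10.7.1 does not decide what happens to FVC, domains or CAT.
3. *The EW visit.* 7.1.4 does not define the time of discontinuation. Section 10.4.1 counts assessments up to the stop date plus 3 days as on-treatment, and Section 10.6.1 can impute a missing stop date as the EW visit date. An EW visit at or near the stop may therefore lie inside the cut for every variable.
4. *SGRQ total against domains.* Section 10.6.3 derives total and domains from one instrument, and its language rule sets all SGRQ scores at a visit to missing together. Table 2.5 prints them together. Only the section heading separates them.
5. *Rescue use.* This is daily diary or sensor data placed in 4-week periods. An end date of its own suits that structure and does not conflict with the visit data.

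**Would a split be hidden?** No. Section 10.5.2 requires the number of participants with every continuous summary. A total computed on fewer participants than its domains would show a smaller n in the same table.

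**Possible size.** Let p be the share of a row's participants who stopped before the announcement and were assessed later, and d the difference between their mean and that of the others.

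- Cut mean = mean of the others (μ).
- Uncut mean = (1 − p)μ + p(μ + d) = μ + p × d.
- Gap = p × d.

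The SAP gives neither p nor d, so both are assumed:

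| p | d = 4 SGRQ points | d = 8 SGRQ points |
|---|---|---|
| 0 | 0 | 0 |
| 10% | 0.4 | 0.8 |
| 20% | 0.8 | 1.6 |
| 30% | 1.2 | 2.4 |

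If p were 10% in one arm and 30% in the other, the difference between the arm means would shift by 0.20 × 4 = 0.8 to 0.20 × 8 = 1.6 points. The efficacy tables are specified as summaries by arm, and none is specified to display that difference.

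**Listings.** Counting Appendix 10 by heading: 5 + 3 + 1 + 2 + 2 + 1 + 3 + 6 + 2 + 6 + 4 + 2 = 37, of which 0 are efficacy listings. The listing sentence in 10.7.1 is therefore broader than the planned output.

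**The case for a change.** The strongest case for a change is that these tables are the whole efficacy output. With few participants and little data from each, a handful of excluded values could be visible. Two programmers could fairly build different tables, because the scope, the cut-off time and the handling of stops at or after the announcement are all unstated. One sentence would settle it and need no new data. If the rule was meant for every efficacy variable, the plan could have said so.

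Much of this stands as description. The section does leave those points unstated, and the listing sentence does not match the planned listings. It does not follow that the plan must change. A programmer building Table 2.5 would apply one rule to scores from one questionnaire, and the same holds for FEV1 and FVC from one spirometry session. Either choice, keeping or dropping later values throughout, is acceptable for a descriptive summary.

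Treating a participant's own decision to stop differently from a stop by the sponsor is also defensible, since the two say different things about the participant. Dropping the restriction to gain uniformity would mix on- and off-treatment values in one row, and extending it would lose values from a small data set. That is a trade-off, not a correction. The listing mismatch is a clerical slip in general wording and alters no summary.

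**Conclusion.** The observation about the text is correct, but the defect it suggests is not established. Section 7.1.4 leaves its scope, its cut-off time and later stops unstated. Different participants behind SGRQ total and its domains would arise only if later data are read as excluded, if a default written for study withdrawal is stretched to treatment discontinuation, and if at least one participant stopped before the announcement and was assessed after the cut-off. The SAP gives no count of such participants.

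Under the assumed ranges (p from 0 to 30%, d of 4 or 8 points), one row's SGRQ mean could move by 0 to 2.4 points, and the differing n would be printed beside it. No hypothesis test or formal efficacy analysis rests on these rows. This is a gap that analysts fill sensibly, together with a clerical mismatch over listings, and no change to the plan is called for.

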7.1.5. Methods

Details of the planned displays are provided in [Appendix 10: List of Data Displays](#) and will be based on GSK data standards and statistical principles.

Unless otherwise specified, endpoints/variables defined in Section [7.1.1](#) will be summarised using descriptive statistics.

7.2. Secondary Efficacy Analyses

7.2.1. Variables

7.2.1.1. Spirometry

Percent predicted FEV₁, FVC (L) and FEV₁/FVC (from clinic spirometry) will be summarized as specified in Section [7.2.2](#).

7.2.1.2. SGRQ Domain Scores

Raw and change from baseline SGRQ Domain scores will be summarized as specified in Section [7.2.2](#).

7.2.1.3. CAT

Raw and change from baseline CAT scores will be summarized as specified in Section [7.2.2](#).

7.2.1.4. Rescue Medication Use

The 4-week mean number of puffs/occasions of rescue use per day and percentage of rescue-free days according to daily eDiary data and MDI sensor data will be summarized as specified in Section [7.2.2](#).

7.2.2. Summary Measure

Summary statistics as specified in Section [10.5.2](#), for percent predicted FEV₁, FVC (L), FEV₁/FVC, SGRQ domain scores and CAT scores by treatment for each time point

Rescue medication use, from both daily diary and MDI sources, will be summarized as mean number of puffs/occasions of rescue use per day and percentage of rescue-free days in 4-week periods as specified in Section [10.6.3](#).

7.2.3. Population of Interest

The summary of secondary endpoints will be based on the Safety population, unless otherwise specified.

7.2.4. Methods

Details of the planned displays are provided in [Appendix 10: List of Data Displays](#) and will be based on GSK data standards and statistical principles.

Unless otherwise specified, variables defined in Section [7.2.1](#) will be summarized using descriptive statistics.

8. SAFETY ANALYSES

All core safety outputs will be reported. The safety analyses will be based on the Safety population, unless otherwise specified.

8.1. Adverse Events Analyses

Adverse events analyses including the analysis of adverse events (AEs), Serious (SAEs) and other significant AEs will be based on GSK Core Data Standards.

8.2. Adverse Events of Special Interest Analyses

AESI have been defined as AEs which have specified areas of interest for the COPD population. A comprehensive list of Standardized Medical Dictionary for Regulatory Activities (MedDRA) terms based on clinical review will be used to identify each type of event. A list is provided in Section [10.6.4](#).

8.3. Clinical Laboratory Analyses

Laboratory evaluations including the analyses of chemistry laboratory tests, haematology laboratory tests, and liver function tests will be based on GSK Core Data Standards. The details of the planned displays are in [Appendix 10: List of Data Displays](#).

8.4. Other Safety Analyses

The analyses of non-laboratory safety test results including ECGs and vital signs will be based on GSK Core Data Standards, unless otherwise specified. The details of the planned displays are presented in [Appendix 10: List of Data Displays](#).

10. APPENDICES

10.1. Appendix 1: Protocol Deviation Management

10.1.1. Protocol Deviation Management

Protocol Deviations in accordance with the most recent Protocol Deviation Management Plan will be tracked by the study team throughout the conduct of the study and at the final protocol deviation review at DBR. Important protocol deviations will be identified and listed as defined in [Appendix 10](#).

10.2. Appendix 2: Schedule of Activities

10.2.1. Protocol Defined Schedule of Events

	Screening/ Visit1 ^a	Visit 2	Visit 3	Visit 4	Visit 5	Visit 6	Visit 7	Visit 8	Visit 9	Visit 10	Visit 11	Visit 12	EW	FU Up to 28 days post last dose
	up to -32 days	Week 0 / D1	Week 2/ D14	Week 4/ D28	Week 8/ D56	Week 12/ D84	Week 16 / D112	Week 20 / D140	Week 24 /D168	Week 32 /D224	Week 40 / D280	Week 52 / D364		
Assessment window		+3d	±3d	±3d	±3d	±3d	±3d	±3d	±3d	±6d	±6d	±6d	±6d	
Eligibility														
Informed Consent	X													
Genetics Informed Consent ^b	X													
Demography	X													
Inclusion and Exclusion Criteria	X													
Smoking Status ^c	X	X												
Smoking History ^c	X													
Medical History ^d	X													
Full physical	X													
Chest X-ray (historical within 1 year acceptable)	X													
HIV, Hepatitis B and C screening ^e	X													
Additional Eligibility and In Study Assessments														
Verify Eligibility ^f	X	X												
Brief physical		X				X			X			X	X	
Laboratory assessments (clinical chemistry, including liver chemistries), haematology, urinalysis	X	X		X					X			X	X	
Additional Liver chemistries only			X		X	X	X	X		X	X			
12 lead ECG	X	X		X		X			X			X	X	
Vital Signs	X	X		X		X			X			X	X	

	Screening/ Visit1 ^a	Visit 2	Visit 3	Visit 4	Visit 5	Visit 6	Visit 7	Visit 8	Visit 9	Visit 10	Visit 11	Visit 12	EW	FU Up to 28 days post last dose
	up to -32 days	Week 0 / D1	Week 2/ D14	Week 4/ D28	Week 8/ D56	Week 12/ D84	Week 16/ D112	Week 20/ D140	Week 24 /D168	Week 32 /D224	Week 40 /D280	Week 52 /D364		
Assessment window		+3d	±3d	±3d	±3d	±3d	±3d	±3d	±3d	±6d	±6d	±6d	±6d	
Genetic, Pharmacokinetic and Biomarker Blood Collections														
Blood sample for Genetics		X												
Blood sample for CRP		X							X			X	X	
Blood sample for exploratory biomarkers		X							X			X	X	

- a Informed consent may be signed prior to screening visit in the case that any changes in medications are necessary
- b Agreeing to genetic sample consent is not required for study participation
- c Smoking status/history assessed at screening; smoking status re-checked at Visit 2
- d Includes substance usage, past and present medical conditions and family history of premature CV disease
- e Hepatitis B (HBsAg) and Hepatitis C (HepC antibody) testing is required. If testing otherwise performed within 3 months prior to the first dose of study treatment, testing at screening is not required. Hepatitis C RNA testing is optional; however a confirmatory negative Hepatitis C RNA test must be obtained, to be able to enrol participants with positive Hepatitis C antibody due to prior resolved disease.
- f Participant's clinical status should be reviewed

10.3. Appendix 3: Assessment Windows

10.3.1. Definitions of Assessment Windows for Analyses

In general, data will be reported according to the nominal time of clinic visits and assessments as specified in the protocol. For example, if a participant recorded values for the Day 28 visit that were actually made on the 21st day of treatment, they will be presented as Day 28 values in the summary tables.

Participants that withdraw from the study at the time of a scheduled study visit will have data collected in the eCRF as part of the scheduled study visit. In order to collect all questionnaires that are scheduled to be performed at the Early Withdrawal (EW) Visit, Patient Reported Outcomes questionnaires completed on the LogPad will be reported as an EW Visit. If the date of the EW questionnaire assessment is the same as the date of a scheduled visit date from the eCRF and there is no questionnaire assessment present at the scheduled visit in question, the EW questionnaire data will be listed, summarized and analysed as part of the scheduled visit.

